SPECIFIC AIMS

Legitimate prescription opioid use during adolescence has been associated with later prescription opioid misuse and substance use disorder symptoms during adulthood.^{1,2} Thus, primary prevention interventions for older adolescents and young adults at the time of prescribing are imperative. With several million opioid prescriptions dispensed to adolescents and young adults each year in the United States,³ providers are uniquely positioned to address and mitigate opioid risks for these vulnerable groups. Indeed, despite a recent plateauing in prescribing rates, opioid-related poisonings, prescription misuse, opioid use disorder and unintentional overdose deaths continue to increase among our youth, suggesting an unrelenting effect of the opioid crisis and an urgent need for action.⁴⁻⁷ Recognizing the urgency for action, state laws have been widely enacted that, among other requirements, mandate informed consent for patients as well as parents of minors who are prescribed opioids. While the intent of such laws is to lessen the impact of the opioid crisis by increasing risk awareness, it is not clear whether such laws are sufficient to enhance risk understanding and mitigate risky behaviors without adversely impacting effective pain management.

We previously demonstrated that opioid risk awareness alone (i.e., knowledge that adverse effects like addiction and excessive sedation can occur) was not related to safer opioid decision-making among parents, whereas higher risk perceptions and analgesic risk avoidance preferences were strongly related.⁸ We have since similarly demonstrated that risk perceptions and analgesic preferences (but not simple risk awareness) were strongly associated with intentions to misuse prescription opioids among a large sample of adolescents and emerging adults.⁹ Finally, desire for pain and other symptom relief remains the most common motive for prescription opioid misuse among adolescents and young adults.^{10,11} Thus, modifiable targets to reduce risky prescription opioid decisions among adolescents/emerging adults include opioid risk perceptions, analgesic risk/benefit preferences and safe pain management knowledge.

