- 2) Examine whether enhanced STOMP messaging will mitigate persistent/recurrent opioid use and later misuse among older adolescents and emerging adults. We hypothesize that opioid misuse risk perceptions mediate the relationship between prescription opioid use and later misuse, and that by enhancing risk perceptions, rates of opioid misuse intentions will decrease.

With adequate funding, we have the unique ability to expand and test translatable strategies that could effectively mitigate adverse outcomes related to opioid prescribing. Our multidisciplinary team's expertise related to opioid risks and pain management practices for youth and opioid misuse, combined with our ability to efficiently recruit and retain research subjects in clinical studies (current loss-to-follow-up is < 15%) supports the natural extension of our current project and will ensure completion within the timeframe of our current grant. This additional work will not only increase the impact of our research, but will lay the necessary foundation for a future longitudinal study of prescription opioid misuse among adolescents and emerging adults.

SIGNIFICANCE OF THIS SUPPLEMENT

Adolescents and emerging adults, themselves, are vulnerable to opioid-related adverse outcomes given high rates of pain and exposure to prescribed opioids. More than 90% of healthy youth report recent pain for which most have self-treated with analgesics.¹³⁻¹⁵

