Our interactive Scenario Tailored Opioid Message Program (STOMP) intervention was developed based on Fuzzy Trace Theory (FTT) with an aim to change the mental model of risk perceptions and shift preferences in a direction that will reduce risky opioid decisions and enhance best analgesic practices. FTT describes how information (both taught and experienced) is processed to create mental representations ranging from precise data to fuzzy or simple gist representations. Based on this theory and consistent with other neurodevelopmental theories, risky decision-making is a function of the mental representations (verbatim and gist) of the options at hand (e.g., to misuse a prescribed drug or not). In addition to mental representations, reward sensitivity (i.e., the degree to which someone is benefit preferent), time preferences (i.e., desire for immediate reward over later ones), and opportunity (i.e., availability) also factor into risky decision-making. Thus, opioid misuse among adolescents and young adults reflects, to varying degrees, the degree to which the risk-taker desires the positive effect of the drug (reward), the ready availability of the drug, and the risk-taker’s cognitive appraisal of the option to misuse (riskiness). While opioid misuse behavior may initially be goal-directed (i.e., to obtain pain relief or benefit), the slippery slope to addiction is sharper

with opioids than, perhaps, other controlled substances. Thus, primary prevention of misuse behavior must begin with initial exposure to the drug. FTT suggests that the most appropriate and, perhaps, most malleable targets to prevent initial opioid misuse are the mental representations of options, that is, of opioid risk perception and analgesic preferences.⁴¹

INNOVATION

- This extension of our parent project is a natural extension of our innovative, interactive STOMP intervention to a group of older adolescents and young adults who are vulnerable to opioid misuse.
- Our intervention aligns with the National Drug Control Strategy with an overall goal to increase risk recognition, prevent opioid-related adverse events and minimize the capacity for future misuse.
- Our intervention uniquely combines scenario-tailored risk decision exercises with tailored risk messages and evidence based advice. Thus, the information has the ability to enhance target perceptions and improve competency or self-efficacy.

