Our sample size is based on our recent findings that 26% of adolescents/young adults indicated a willingness to misuse a prescribed opioid for pain management. We need 426 participants (142/group) to detect a clinically important effect of the STOMP intervention on misuse intention (i.e., decrease to 13%; 95% confidence and 80% power). This sample will be more than sufficient to detect an expected mean difference in opioid misuse risk perception between either intervention group and the control (MD 0.56, SD 1.21; sample needed = 122) and to test for a modest effect of the interventions in a factorial design (estimated eta squared 0.14; sample needed = 147). To allow for 30% loss to follow-up and to account for missing data, we will recruit up to 600 participants.

Table 1. Sequence of study assessments

Measures	Time 0 Baseline (preop)	Time 0.1 (Immediately Post-Session)	Time 1 (7 days)	Time 2 (14 days)	Time 3 (1 month)	Time 4 (3 months)
Demographics	x					
Pain, Analgesic and Misuse History	x					
Pain relief Preference	x			x		
Opioid knowledge/ risk perceptions	x	x		x	x	x
Opioid misuse risk perceptions	x	x		x	x	x
Scenario (situational) decision-making	x			x	x	x
Analgesic self-efficacy	x	x				
Pain interference			x	x	x	x
Opioid left-over disposal				x	x	x

Analgesic use and ADEs			x	x	x	x
Perioperative data	x					
Analgesic refill data				x		

DATA ANALYSES

Generalized estimating equations (GEE) will be used to model both continuous (i.e., negative binomial and Gaussian) and binary outcomes (i.e., binomial) for each aim.^{151,152} All models will include both time-varying measures (e.g., opioid risk perceptions) and time-invariant covariates (e.g., sex, race, etc.) and will use either an independent or exchangeable correlation structure to correct for within subject correlations. Analyses will use Stata's (STATA/SE v.13; STATA Corp., College Station, TX) 'xtgee' option as appropriate. All hypotheses per our conceptual model (Figure 3) will be tested at the 0.05 alpha level. Standardized coefficients and adjusted odds ratios will be computed to determine the relative effect size for each of the key independent variables.

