Missing data: The use of electronic surveys with built-in prompts for incomplete items will reduce the potential for missing responses. Patients will be contacted by phone, text or email (per their preference) to promote ongoing recording of postoperative data and to reduce the potential for missing data and LTF. We have used similar procedures to successfully ensure complete data and minimize loss to follow-up.^{8,25,94,153}

Any remaining missing data on surveys (e.g., assist or PR-Pref) will be examined for randomness and we will impute only partial non-response (e.g., missing 1 to 2 items of PR-Pref or assist) using a horizontal (i.e., per individual) approach. Largely incomplete or total survey non-response will be examined for non-randomness and potential bias (e.g., missing DAST-10). These missing data will not be imputed, however, outcomes will be compared for persons with missing vs. complete data to determine selection bias. We have adjusted our sample size to account for the potential for missing data. We will use pairwise deletion to use the available, complete cases to test our hypotheses.

Aim 1: Using GEE, we will examine the association between the STOMP intervention and the outcomes (risk seriousness perception, and situational opioid decisions). It is hypothesized that, compared to controls, patients who receive the STOMP intervention will have 1) enhanced risk perceptions (continuous measure) and 2) improved opioid decisions (scenario-based). Hypotheses 1 and 2 will be tested using both main and interaction effect models. In the main effects models, STOMP group assignment is our binary independent variable of interest. Time by intervention interaction effect models will be used to examine whether the STOMP group has improved opioid risk perceptions and decisions at the follow-up assessments compared to the control group. It is expected that there will be no difference between the intervention group and control group at baseline. However, significant interaction effect terms should emerge for the intervention group at the follow-up assessments.

Anticipated Problems and Solutions:

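### As worded, the GEE rule adjusts the H2 test of STOMP on misuse intentions for follow-up risk perceptions, which STOMP is designed to change

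*Combined protocol and SAP*

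**What the plan says.** The opening paragraph of Data Analyses applies GEE to continuous and binary outcomes under every aim. It then states: "All models will include both time-varying measures (e.g., opioid risk perceptions) and time-invariant covariates". Risk perceptions are the only time-varying example. The same paragraph adds that "adjusted odds ratios will be computed to determine the relative effect size for each of the key independent variables".

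The Aim 1 paragraph lists two outcomes, risk perception and scenario-based opioid decisions. For the main-effects models it says that "STOMP group assignment is our binary independent variable of interest". For the time-by-intervention models it expects that "significant interaction effect terms should emerge for the intervention group at the follow-up assessments". It gives no covariate list.

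Elsewhere the document places risk perception on the causal route from STOMP to decisions:

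- Specific Aims: "modifiable targets to reduce risky prescription opioid decisions among adolescents/emerging adults include opioid risk perceptions".
- Specific Aims, second aim: "by enhancing risk perceptions, rates of opioid misuse intentions will decrease".
- Scientific Premise, on what can be changed: "targets to prevent initial opioid misuse are the mental representations of options, that is, of opioid risk perception and analgesic preferences".

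Table 1 schedules both risk-perception measures at baseline, immediately after the session, 14 days, 1 month and 3 months. Scenario decisions are scheduled at baseline, 14 days, 1 month and 3 months.

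**The concern.** A time-varying risk-perception covariate in the H2 model is, at each follow-up visit, a post-randomisation measurement of something STOMP is intended to raise. Two problems follow.

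First, the estimand changes. The STOMP coefficient no longer measures the total effect of being assigned to STOMP. It measures what remains after removing whatever passes through same-visit perception, which is the part the theory says matters most.

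Second, the contrast loses the protection of randomisation. The Significance section reports a strong association between perceived misuse risk and misuse intention, and says past misuse helps explain intention. Arms are balanced on past misuse overall, but not within levels of follow-up perception. Suppose past misuse lowers perceived risk and raises intention. Then, at the same follow-up perception score, STOMP participants will tend to include more past misusers than controls, which biases the adjusted effect towards no benefit.

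Other time-varying measures raise the same question. Pain relief preference is repeated at 14 days, and the Scientific Premise names analgesic preferences as a target too.

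**Working it through.** **1. The plan's own figure.** Sample Size Determination gives 142 per group (426 in all) for 26% versus 13% at 80% power; alpha is 0.05. The unpooled two-sided formula gives

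n = (1.960 + 0.842)² × (0.26×0.74 + 0.13×0.87) / 0.13² = 7.849 × 0.3055 / 0.0169 = 141.9, so 142 per group and 3 × 142 = 426.

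The figure reproduces. It rests on the total effect: OR = (0.13/0.87)/(0.26/0.74) = 0.425, log-OR −0.855. No perception covariate enters it.

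**2. The passages side by side.** The rule covers all models. It cannot hold for the risk-perception outcome (H1), because a variable cannot be a covariate for itself. It can hold for H2, and Table 1 supplies a same-visit perception value at every decision visit. No section says that H2 uses baseline perception only. No mediation model appears in the analysis text to which the sentence could belong.

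**3. Size: an illustration.** From the document: 26%, 13%, 142 per group, and the expected shift in misuse risk perception (mean difference 0.56, SD 1.21). Assumed:

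- Perception M is normal with SD 1.21, correlation 0.5 across visits, and is shifted by 0.56 in STOMP participants at follow-up.
- logit P(misuse intention) = a + d·(STOMP at follow-up) + b·M. Here a and d are set so that the marginal follow-up rates stay at 26% and 13%, with 26% in both arms at baseline. The perception-adjusted STOMP OR is exp(d).
- exp(b), the link per perception point, is 0.85, 0.74, 0.55 or 0.37. Per SD this is exp(b)^1.21 = 0.82, 0.69, 0.49 or 0.30; the last is extreme.
- Within-person decision correlation is about 0.35 to 0.39.
- GEE with independence working correlation and robust standard errors, two-sided 0.05, 2,500 replicates (4,000 for the single visit). The largest simulation standard error is √(0.25/2500) = 1 percentage point.

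| Link, OR per point | 0.85 | 0.74 | 0.55 | 0.37 | Without covariate |
|---|---|---|---|---|---|
| Rate if only perception acted (from 26%) | 24.3% | 23.0% | 20.5% | 18.2% | – |
| Adjusted STOMP OR | 0.463 | 0.495 | 0.555 | 0.620 | 0.425 |
| ln(adjusted OR) / −0.855 | 90% | 82% | 69% | 56% | 100% |
| Power, main effects, 284 vs 142 | 97.1% | 93.3% | 81.9% | 60.8% | 99.0–99.4% |
| Power, arm-by-time, joint 3 df, 284 vs 142 | 84.0% | 75.6% | 53.2% | 31.9% | 91.3–92.3% |
| Power, arm-by-follow-up, 1 df, 284 vs 142 | 93.1% | 87.6% | 71.0% | 45.7% | 97.1–97.4% |
| Power, main effects, 142 vs 142 | 90.2% | 83.9% | 67.0% | 45.7% | 95.7–96.2% |
| Power, arm-by-time, joint 3 df, 142 vs 142 | 68.3% | 57.0% | 38.5% | 23.3% | 78.0–79.5% |
| Power, single visit, 142 vs 142 | 67.8% | 60.2% | 43.3% | 28.5% | 79.1–80.2% |

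The main-effects rows use the three follow-up visits; the arm-by-time rows add baseline. The log-OR ratio is not a pure mediated share, because odds ratios are non-collapsible.

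**4. Sensitivity.** With decision correlation 0.40 to 0.44, pooled main-effects power at the last three links is 92.4%, 77.2% and 57.7%. With half the perception shift (0.28), pooled, the adjusted OR is 0.443, 0.455, 0.470 and 0.469. Main-effects power is then 98.6%, 97.8%, 96.0% and 94.7%, and joint arm-by-time power is 89.2%, 85.6%, 78.1% and 70.5%.

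**5. Upper bound.** If intention were a fixed threshold on perception, the shift alone would give Φ(Φ⁻¹(0.26) − 0.56/1.21) = Φ(−0.643 − 0.463) = 0.134. Even that limit falls just short of 13%, so a nil adjusted effect is not expected. The model contains no common cause of perception and intention, so the confounding described above is not counted.

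**The case against.** The strongest reply is that the plan never meant this model. The sentence calls the time-varying items measures and reserves the word covariates for the time-invariant ones. A repeated outcome is also a time-varying measure, so the sentence may only describe the data structure. The Aim 1 paragraph treats perceptions and decisions as parallel outcomes, with STOMP assignment as the exposure, which points to a total-effect test. Adjusted odds ratios need mean no more than control for sex and race, which the document promises elsewhere. The conceptual model (Figure 3) is not shown in the available text, and the supplement leans on a parent project.

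Part of this stands. The intent is ambiguous, the promise of adjusted odds ratios proves nothing by itself, and no inference is drawn from the missing figure. But what a model includes is ordinarily its predictors, and the paragraph goes on to speak of independent variables. Reading the sentence as a description of outcomes is strained, and an analyst could reasonably follow it as a rule.

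The second reply concerns size, and it largely stands. The link and the correlations are assumed. The 0.56 shift belongs to misuse risk perception, a separate row of Table 1 from the general risk perceptions that the sentence groups together. On the pooled main-effects test, power stays above 80% at three of the four links. The heaviest losses come from a 3-df joint test that the plan does not specify; a 1-df term loses less. The case therefore rests on the estimand and on lost protection from confounding, not on a particular power figure.

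**Conclusion.** The concern holds: for H2 the rule is wrong as written and should be fixed, with medium confidence because the authors' intent is unclear. If it is followed, H2 tests a smaller, partly direct and no longer randomisation-protected effect, instead of the total effect on which 142 per group was calculated. The extent cannot be derived from the document. Under the stated assumptions the adjusted OR lies between 0.46 and 0.62, and the cost runs from slight (pooled main effects, weak link) to serious (arm-by-time, strong link). The sample size itself is not in dispute. The specification fault does not depend on the assumed links: two analysts reading the same sentence could report different H2 effects.

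**What to change.** Reword the sentence in Data Analyses. State that the models testing the STOMP effect (H1 and H2) contain arm, time, arm-by-time and baseline covariates recorded before any STOMP message is shown, and no post-randomisation measure that STOMP may change. Place follow-up risk perceptions in a separate, labelled mediation analysis for the second-aim hypothesis. That analysis should state its no-confounding assumption for perception and intention and adjust for baseline misuse history, which Table 1 already collects. The cost is SAP wording only: no new data and no extra participants.

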Our current research (R01DA044245) examines the ability of our interactive Scenario Tailored Opioid Messaging Program (STOMP) to shift these modifiable factors in a way that will improve parental opioid decision making and handling while simultaneously ensuring good pain management of their children. This intervention, thus, provides an innovative, balanced approach to address both the primary prevention of opioid-related adverse outcomes and effective pain management. Relevant to this supplement, we will modify STOMP messages and test their impact on opioid risk perceptions and risky decision-making among older adolescents and emerging adults who make most if not all analgesic treatment decisions for themselves.

Supplemental funding via PA-18-591 will enable us to expand the target population of our current project to include older adolescents and emerging adults who are prescribed opioids for an acute pain condition and who are among those at highest risk for misuse. Specifically, funding will allow us to modify our STOMP messages to address the risks of opioid misuse and personal strategies to manage symptoms, and compare the effect of these STOMP messages to routine opioid analgesic consent information. These objectives fall within the scope of our currently funded project, but effectively expand our target enrollment to address the high priority need for primary prevention among youth. Thus, with supplemental funding, we aim to test the following hypothesis:

- 1) Examine whether modified STOMP messages will improve opioid risk understanding, enhance misuse risk perceptions, improve analgesic self-efficacy, and opioid decision-making among older adolescents and emerging adults (ages 15-24) who are prescribed opioids for post-procedure pain management. We hypothesize that older adolescents and young adults who are randomized to the intervention (versus routine opioid information/consent) will exhibit; **(H1)** Greater and sustained understanding of the potential risks of opioid misuse **(H2)** Decreased intentions to medically or non-medically misuse opioids for personal use, or share (divert) personal prescriptions with others.

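### The Aim 1 GEE plan names no robust variance, credits an independent working structure with a correction it does not make, and does not state the outcome visits of the main-effects model

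*Combined protocol and SAP*

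**What the plan says.** DATA ANALYSES specifies GEE for every aim. All models "will use either an independent or exchangeable correlation structure to correct for within subject correlations". No rule chooses between the two structures. On software it says only "Analyses will use Stata's (STATA/SE v.13; STATA Corp., College Station, TX) 'xtgee' option as appropriate". On significance: "All hypotheses per our conceptual model (Figure 3) will be tested at the 0.05 alpha level". No robust, sandwich, empirical or bootstrap variance is named anywhere in the document.

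The Aim 1 paragraph continues: "Hypotheses 1 and 2 will be tested using both main and interaction effect models". For the first kind of model it gives one detail: "In the main effects models, STOMP group assignment is our binary independent variable of interest". It does not say whether Time 0 is an outcome row, a covariate or left out. For the interaction model it expects no group difference at baseline and that "significant interaction effect terms should emerge for the intervention group at the follow-up assessments".

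Table 1 schedules scenario decisions at four times (baseline, 14 days, 1 month, 3 months). It schedules misuse risk perceptions at five (the same four plus immediately after the session). H1 in SPECIFIC AIMS is "Greater and sustained understanding of the potential risks of opioid misuse".

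**The concern.** An independent working structure treats a participant's repeated answers as if they came from different people. With a participant-clustered robust variance that is a legitimate choice. With model-based standard errors it is not: the group effect looks too precise, and the within-person changes look too imprecise. The plan gives the structure itself as the correction and names nothing else, so an analyst could follow the text to the letter and report invalid p-values for H1 and H2.

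The second gap is the set of outcome rows. Nobody has had any effect of the intervention at a true baseline. If Time 0 rows enter a model with a single group term, the estimate averages a zero effect with the follow-up effects. Because Table 1 collects both outcomes at Time 0, this is a live choice.

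**Working it through.** **Inputs from the documents.** 26% versus 13%, 142 per group, 80% power, alpha 0.05 (Sample Size Determination); 4 visits for decisions and 5 for risk perceptions, baseline included (Table 1).

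**Assumptions.** Two-sided tests, complete data, no covariates, and within-subject correlation ρ, for which the documents give no value. I use 0.3/0.5/0.7. For H2 power I use 0.3/0.5/0.6, because yes/no answers with rates of 26% and 13% cannot correlate above √(0.13×0.74/(0.87×0.26)) = 0.65.

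**Plan's own figure.** n = (1.96+0.84)²×(0.26×0.74+0.13×0.87)/0.13² = 141.9, so 142 per group and 426 in all. It reproduces. It is a single-time-point calculation, so it does not settle how the repeated answers are analysed.

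**1. Independence with model-based errors, group main effect.** The true variance is D = 1+(m−1)ρ times the reported one, where m is the number of visits. Type I error = 2×[1−Φ(1.96/√D)].

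| Visits in the model | D at ρ 0.3/0.5/0.7 | Type I error |
|---|---|---|
| 3 (decisions, follow-up only) | 1.6/2.0/2.4 | 12/17/21% |
| 4 (decisions with Time 0, or risk perceptions follow-up only) | 1.9/2.5/3.1 | 16/22/27% |
| 5 (risk perceptions with Time 0) | 2.2/3.0/3.8 | 19/26/31% |

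Dropping Time 0 rows does not cure it.

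**2. Same choice, time-by-group term.** Here D = 1−ρ, so the error runs the other way: 1.9/0.6/0.03%.

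**3. Exchangeable with model-based errors.** If the correlation really is equal across visits, tests sit near 5%. Suppose instead that it decays by visit, r^lag. Let a be the mean pairwise correlation. The 3-month-minus-Time-0 interaction has D = (1−r^(k−1))/(1−a) with k visits.

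| k | a at r 0.3/0.5/0.7 | D | Type I error |
|---|---|---|---|
| 4 | 0.18/0.35/0.57 | 1.19/1.35/1.53 | 7/9/11% |
| 5 | 0.15/0.31/0.52 | 1.17/1.35/1.58 | 7/9/12% |

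The group main effect is hardly touched.

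**4. Simulation check** (logistic GEE, 4 visits, no true effect, 142 per group, two STOMP groups pooled against control, 1,000 runs per scenario).
- Equal correlation of about 0.46: independence with model-based errors gave 20.7% for the main effect and 1.2% for the last-visit interaction.
- Decaying correlation of 0.64/0.49/0.40: the same choice gave 23.9% and 0.4%. Exchangeable with model-based errors gave 6.0% (main effect) and 8.0% (last-visit interaction).
- Robust errors gave 3.8-6.1% throughout.

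**5. Time 0 rows in the main-effects model.** A constant follow-up effect is averaged to 3/4 for decisions: 13×3/4 = 9.75 points. The STOMP average becomes (26+3×13)/4 = 16.25%, and the odds ratio moves from 0.43 to 0.55. For risk perceptions the factor is 4/5: 0.56×4/5 = 0.45.

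H2 power uses the difference in logits of the visit-averaged rates with a delta-method standard error. For 142 versus 142 and ρ 0.5, the difference is 0.594 and the standard error 0.233, so power = Φ(0.594/0.233−1.96) = 72%.

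| Main-effects model for H2 | Power at ρ 0.3/0.5/0.6 |
|---|---|
| Time 0 rows in, equal visit weights, 142 v 142 | 83/72/67% |
| Same, STOMP arms pooled, 284 v 142 | 93/86/82% |
| Time 0 rows in, exchangeable with visit indicators, 142 v 142 (simulated) | 80/64/54% |
| Same, pooled (large-sample GEE) | 90/74/61% |
| Follow-up rows only, 142 v 142 | 96/91/89% |
| Follow-up rows plus Time 0 covariate, 142 v 142 (simulated) | about 99% |

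The exchangeable rows are lower because the visits have unequal variances and Time 0 gets more weight. The average follow-up-minus-baseline interaction contrast is undiluted: 88/95/98% for 142 v 142. Risk-perception power with Time 0 rows in stays at 95% or more for ρ up to 0.7.

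**The case against.** The strongest reply is that the large error rates need two choices together, an independent structure and model-based errors, and the plan states only that the first is possible. It aims to handle the correlation, and its open wording about the software leaves room for a robust option. The parent plan, which is not shown, may name one. This stands: a reader might infer that the plan's group test has 16-31% type I error, but the documents do not commit to that test. What remains is a gap together with a stated rationale that is wrong.

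A reader might also infer that exchangeable is unsafe whenever its form is wrong. That is too broad. The group main effect stays near 5%, and only visit-specific interaction terms are affected.

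A third tempting reading is that the trial loses its planned power. It does not follow. The text does not say that Time 0 rows enter the main-effects model. The group term is binary, and for pooled STOMP against control with equal visit weights power stays above 80%. The interaction model is not diluted at all. Falling below 80% needs Time 0 rows plus either a 142 v 142 comparison or the exchangeable structure with visit indicators.

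The power figures also leave out the covariates and missing data that the planned models will have. Adding the Time 0 value to the interaction model would be an efficiency gain, not a correction.

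**Conclusion.** The concern holds as a specification gap with one incorrect statement. Independence does not correct for within-subject correlation. Unless a robust variance is required, the text permits a group test with roughly three to six times its nominal error, and time-by-group tests that are far too conservative. Under exchangeable the exposure is limited to visit-specific terms, about 7-12% at 3 months if correlation decays.

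The unstated outcome visits are a separate gap that bears mainly on H2 power, and only if Time 0 rows are used as outcomes in the main-effects model.

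All sizes rest on assumed correlations, complete data and no covariates. The direction of each error does not depend on the value chosen, provided answers from the same participant are positively correlated. This should be fixed before analysis, but it does not show that a wrong analysis is planned.

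**What to change.** 1. Require standard errors that are robust and clustered on participant in every xtgee model, whichever working structure is used. Delete the claim that an independent structure corrects for correlation. If the parent plan already requires robust errors, say so here.
2. State the outcome visits of the main-effects model: post-baseline visits, with the Time 0 value of the same measure as covariate, or a constrained-baseline model. First confirm from the survey build that Time 0 decision answers were recorded before any STOMP screen, because Study Procedures places the feedback alongside each decision exercise inside the survey. If that cannot be confirmed, use follow-up rows only for decisions, without the Time 0 covariate.
3. Test H1 and H2 by the average post-baseline group contrast. Judge persistence by the group contrast at 3 months. Do not use a group-by-time term in the post-baseline model for this: a perfectly sustained effect produces no such interaction, and a significant term shows only that the effect changed.

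The cost is wording, one variance option and one check of the survey build, with no new data. The covariate form loses participants without a Time 0 value; the constrained-baseline form keeps them.
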